7.3 Secondary Outcome(s) Analyses

For each secondary outcome except the adult household contact viral acquisition, the population of interest is the ITT population, with assigned treatment arm used, even if it differs from administered treatment arm. The viral acquisition outcome is further restricted to households with at least two adults for which no other adult besides the index study subject is positive for COVID-19 at baseline.

7.3.1 14-day Hospitalization

The comparison of proportion of patients hospitalized by $DayR+13$ between the randomized hydroxychloroquine and placebo groups will be performed with a two-sided Cochran-Mantel-Haenszel (CMH) test stratifying by the age categories as used for randomization, with 2-sided $\alpha=0.05$. As noted in Section 5.4, in the unlikely event that some patients die within 14 days after randomization without being hospitalized, these patients will be assigned to the hospitalization category in the analysis. Results will be presented as relative risks with 95% confidence intervals within each age stratum, and then pooled across strata. The pooled estimator is the estimator for the principal analysis.

7.3.2 Average of COVID-19 attributable symptoms

As noted in Section 2.1.3 of this SAP, the average symptom level of COVID-19-attributable symptoms was not originally an outcome in the protocol, but the PIs agreed to make this a secondary outcome and change the symptom duration outcome to be an exploratory outcome.

The average symptom level of the core symptoms will be analyzed as an average level for the 15 daily assessments, $DayA1$ – $DayA15$. Missingness in outcomes is particularly acute because the univariate outcome is the average of 15 assessments. The following approach, which combines multiple imputation and the last value carried forward (LVCF), will therefore be taken.

1. Restrict the data to individuals who did not die on or before $DayA1$ and who have at least one nonmissing daily average from among the following collection of assessments: Baseline, $DayA1$, $DayA2$, ..., $DayA15$.
2. For each participant, determine which of $DayA1$ – $DayA15$ meet all of the following conditions: (a) the participant was hospitalized on at least some portion of the day, AND (b) the participant is not known to have died that day, AND (c) the participant's

daily symptom average is missing, as described in Section 5.4. If there are any such days, then

- Beginning at the earliest such day, determine if the immediately preceding period (i.e., baseline if for $DayA1$, $DayA1$ if for $DayA2$, etc.) had a nonmissing value. If so, assign the previous symptom average score to be the missing day's average and move to the next such day to determine if it will propagate a value forward or not. If not, leave the day as missing and proceed to the next such day to determine if it will propagate a value forward or not.

3. Impute any remaining missing values (whether hospitalized, dead, or not), separately for each ITT treatment arm, using chained equations with the following variables: daily core average from the baseline assessment and assessment days 1–15, comorbidity presence, age group, sex, ethnicity, and race. The imputation will be conducted in IVEware and will use an R-squared entry criterion of 0.01 for each variable's imputation; a minimum of 10 imputed data sets will be generated.
4. Post-process values that had been imputed during hospitalization by applying LVCF; the value to carry forward is from the most-recent period that (a) has an observed average score AND was earlier in the same hospitalization, if any, or otherwise (b) was the (possibly imputed) assessment period immediately before hospitalization. If there is no previous assessment because the hospitalization was before the baseline assessment, carry forward the imputed baseline value while the hospitalization is ongoing or through the period immediately before a nonmissing average was observed, whichever occurs first.
5. Calculate the average value for $DayA1$ – $DayA15$. If the individual died on or before $DayA15$, average only the values from $DayA1$ to the day before death, inclusive.

The outcome will be modeled with linear regression while adjusting for the baseline average, age group, comorbidity presence, treatment, sex, race, ethnicity, and age group \times comorbidity interaction effects. Rubin's rules will be used to make final inference, with interest on the two-sided p-value for the treatment effect, which will be declared statistically significant if < 0.05 .

As with the imputation model, the main analysis model for the average symptom level will be restricted to ITT subjects who had at least one observed symptom average from among the baseline or $DayA1$ – $DayA15$ measurements.

7.3.3 Persistence of Viral Shedding on Day 28

This analysis will omit subjects known to have died on or before $DayR + 30$ without having a Day 28 swab result. (The Day 28 swab may be in a ± 2 day window, so a participant may

have a “Day 28” swab even if the subject died on *DayD28*.) Some missing data will be assumed positive or negative, as described for this day 28 shedding outcome in Section 5.4. Then, multiple imputation will be employed for subjects with still-missing values for the Day 28 viral shedding outcome. There will be a minimum of $m = 10$ imputed datasets, and variables used to impute the outcome will include variables such as prior hospitalizations while on study, treatment arm (if imputation is not already stratified by treatment arm), age group, and viral shedding history.

Comparison of the proportion of index subjects with Day 28 viral shedding between the randomized hydroxychloroquine and placebo groups will be performed. This will be based on the Cochran-Mantel-Haenszel test statistic when stratifying by the age categories as used for randomization. It is desired to employ a test statistic that is approximately normally distributed under the null hypothesis of no treatment effect so that Rubin’s rules may be used to make inference across imputations. Therefore, the signed square root of the CMH test statistic will be calculated for each imputation (negative if and only if the CMH odds ratio for the imputed data set is < 1). The two-sided test will use $\alpha=0.05$.

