7.4.5 Quality of life (EQ-5D-5L Assessment)

The EQ-5D-5L quality of life assessment is administered at baseline, 28 days, and 6 months and we will analyze the VAS and an index measure, as described in Section 5.4. Multiple imputation of missing values will be implemented prior to analysis to improve inference given the expectation that missingness may depend on other characteristics. Imputation will include a death indicator for subjects who were known to have died before the assessment was to have occurred. After imputation, differences between day 28 (6 months) and baseline values of the VAS will be calculated. Any subjects whose measurement at day 28 (6 months) is missing because the individual died will then be post-processed to have a value worse than the worst possible difference among survivors (i.e., -101). Mean differences between day 28 (month 6) values and baseline will be compared between arms using a suitable approach (e.g., Van Elteren test), while adjusting for age stratum.

A similar analytical approach will be taken for the EQ-5D-5L index measure, except that the index measure will be set to 0 for individuals who were missing the assessment because they were deceased. No other missing index measure values will be imputed. Note that survivors may have a lower value for this index measure (i.e., <0) than those who are deceased.

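### The symptom-score imputation omits hospitalization from its predictors, so missing days of admitted participants are filled in as if they had not been admitted, given their other scores (SAP 7.3.2)

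*SAP*

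**What the plan says.** The outcome is the mean of the daily core-symptom averages over DayA1 to DayA15, on a 0–5 scale. SAP 7.3.2 fills in missing days as follows.

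- **Step 2**, before any imputation, looks at each missing hospital day and at the period just before it. If that period has a score: "If so, assign the previous symptom average score to be the missing day's average".
- **Step 3** deals with everything still missing: "Impute any remaining missing values (whether hospitalized, dead, or not), separately for each ITT treatment arm, using chained equations with the following variables". The variables are then listed: "daily core average from the baseline assessment and assessment days 1–15, comorbidity presence, age group, sex, ethnicity, and race". A variable enters an equation only if it passes an R-squared criterion of 0.01.
- **Step 4** overwrites values imputed during a stay. First choice is a period that "has an observed average score AND was earlier in the same hospitalization, if any"; failing that, the one that "was the (possibly imputed) assessment period immediately before hospitalization".
- **Step 5** averages the days, leaving out the day of death and later.

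The treatment effect is then tested at two-sided 0.05. Section 7.3.2 gives no sensitivity analysis for this fill-in.

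Other imputation models in the SAP use such information. For Day 28 shedding (7.3.3) the model "will include variables such as prior hospitalizations while on study". For the EQ-5D-5L (7.4.5): "Imputation will include a death indicator".

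**The concern.** Admission plausibly marks both worse symptoms and missed surveys. An imputation that ignores it assumes that, once the listed variables are known, an admitted participant's missing score behaves like anyone else's. That is hard to defend for people who fell ill enough to be admitted, and the fit is dominated by people who were never admitted.

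The information is at hand. Under SAP 5.4, 14-day hospitalization comes from chart review, study assessments or death. It is missing only when a participant was lost to follow-up and withdrawal bars chart review. Steps 2 and 4 cannot run without day-level hospital status. The SAP also treats a hospital day as swab-positive for the primary outcome and as symptomatic for symptom duration.

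At stake is a tested secondary outcome. If the arms differ in admissions, or in how often admitted participants stop responding, the arm with more such participants would look better than it should. Reduced hospitalization is part of the study hypothesis (protocol 2.3), so equal admission rates cannot be presumed.

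**Working it through.** **1. Which missing days are affected**

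| Missing day of an admitted participant | Filled by | Affected by the omission? |
|---|---|---|
| Hospital day, with an observed score on the day before admission or earlier in the stay | Carry-forward of that score (step 2 or 4(a)) | No |
| Hospital day, with neither | Step 3, then overwritten by the imputed pre-admission value (step 4(b)) | Yes |
| Day before admission | Step 3 | Yes |
| Day after discharge | Step 3, not revisited | Yes |

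**2. One participant traced.** Suppose the last answer is on day 2, the stay is days 5–9, and there are no later answers. Days 3–4 are imputed (2 days). Days 5–9 inherit the imputed day 4 (5 days). Days 10–15 are imputed (6 days). So 2 + 5 + 6 = 13 of the 15 averaged days come from a model without the admission.

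**3. Size by arithmetic.** The documents give no figure for this outcome to reproduce; protocol Table 2 concerns the primary outcome only. With the same q, d and g in both arms:

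bias in the arm difference ≈ (p₁ − p₂) × q × (d/15) × g

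Here p is the proportion admitted, q the share of them who are silent, d the affected days, and g the true score minus the filled-in score. The 15 and the 0–5 scale are from the SAP; all else is assumed.

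- All 13 days one point too low: (0.08 − 0.03) × 0.5 × 13/15 × 1 = 0.022.
- Only the five hospital days one point too low: 0.05 × 0.5 × 5/15 × 1 = 0.008.
- Range for the same 5-point difference in admissions: 0.05 × 0.3 × 4/15 × 1 = 0.004; 0.05 × 0.6 × 6/15 × 2 = 0.024; 0.05 × 1 × 10/15 × 3 = 0.10.
- Equal admission and equal non-response: 0.
- Equal admission of 5%, but 60% versus 30% silent (d = 6, g = 2): 0.024 − 0.012 = 0.012.

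**4. Simulation of steps 2–4, one arm of 200.** Assumptions: scores of admitted participants rise by 1.5 points from two days before admission through the stay; silent participants miss every survey from three days before admission to discharge. There were 40 runs per scenario and five imputations. The R-squared rule was not modelled. Mean in-hospital score of silent participants:

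| Admitted / silent | True | As written | With indicator |
|---|---|---|---|
| 3% / 60% | 2.232 | 1.095 | 1.664 |
| 5% / 60% | 2.252 | 1.149 | 1.541 |
| 10% / 60% | 2.251 | 1.191 | 1.555 |
| 5% / 100% | 2.281 | 1.088 | 1.836 |

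In the 5% / 60% scenario, never-admitted participants averaged about 0.81 (days 4–11). Admitted participants outside the silent group were filled in at 2.388 against a true 2.281. The whole-arm mean was 0.860 true, 0.843 as written (0.017 too low) and 0.849 with the indicator (0.011 too low).

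**5. Simulation of the arm difference**, on assumed trajectories, 200 per arm, imputed by arm, again without the R-squared rule. With 8% versus 3% admitted the bias was about −0.014 as written and −0.004 with the indicator. With 5% in both arms it was near zero either way. The error SD was smaller with the indicator in every case.

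**The case against.** A reader might infer that admitted non-responders are filled in as though they had stayed well at home. The documents do not support that. Step 3 conditions on each person's own baseline and daily scores, comorbidity and age group, so someone who was ill when last observed is not imputed as well. In the simulation, silent participants were filled in at about 1.1 to 1.2, above the 0.8 of never-admitted participants, though well below the true 2.2 to 2.3. Nor are all admitted participants affected: observed scores just before or during the stay take precedence.

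Four further objections deserve an answer.

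- **The effect is small and assumed.** This stands. The protocol expects few hospitalizations, and a treatment that changes neither admission nor response leaves no expected bias in the comparison.
- **The indicator would be unstable.** At 3% of 200 there are about 6 admissions per arm, perhaps half of them silent. The coefficient will be imprecise, but in the simulation of the arm difference the overall error fell rather than rose.
- **The contrasts with other sections are weak.** Partly right. The death indicator in 7.4.5 has little bearing, because step 5 already drops days from death onward. Section 7.3.3 imputes one binary result and names its variables only as examples. It still shows that the SAP regards admission as usable and informative.
- **It is late to change the model.** The SAP's change log for version 1.4 says that the primary manuscript had been drafted and refers to results already viewed. This limits how a rerun can be presented; it does not make the omission sound.

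**Conclusion.** The point holds as a modest one. The step 3 list omits hospitalization, and the missing days identified above are imputed as if the participant had not been admitted, given their other scores. The likely direction is too low.

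Bias in the treatment difference needs admission or non-response to differ by arm. With 3% versus 8% admitted, it is about 0.01 to 0.02 points on the 0–5 scale. More extreme assumptions reach 0.10, and balanced arms give about zero. No SD is stated for the score, so these shifts cannot be turned into an effect on power or type I error.

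Two stronger inferences should be resisted: that the secondary result is materially wrong, and that one added predictor would remove the bias. The simulations show that the bias shrinks but remains, because steps 2 and 4 still hold hospital days at the pre-admission level.

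**What to change.** Add to the step 3 predictors an indicator of hospitalization on or before DayA15, and keep imputation by arm where possible, as SAP 5.2 requires. Build it from the day-level stay dates that steps 2 and 4 need. The 14-day hospitalization outcome stops at DayR+13, whereas DayA15 will usually fall on DayR+15 (DayA1 = DayR+1, plus 14). State whether the indicator is exempt from the R-squared entry rule; the simulated gain assumes that it is always in the model.

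Add a delta-adjusted sensitivity analysis. After step 4, shift the imputed scores of admitted participants upward once, including imputed values carried through a stay, for example by 1, 2 and 3 points capped at 5, and repeat the regression. With few admissions this will tell more than the indicator.

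Label any rerun after results were viewed as post hoc, as SAP 1.2 requires of analyses not in the plan.

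The cost is one predictor, a sentence or two in the SAP and one extra set of runs. The coefficient will be imprecise if admissions are few, and the bias is reduced, not removed.

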5.5 Independent Review

All statistical analyses for primary reporting of trial results will be independently verified through dual programming. Two statisticians will each program all datasets and analyses for the DSMB reports and the primary manuscript(s) and the results will be compared.

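### A floor of 10 imputations before two secondary 0.05 tests lets a borderline p-value turn on the random seed; 100 would cost only computing time

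*SAP*

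**What the plan says.** SAP 7.3.2 (average symptom level) imputes by chained equations within each arm and states "a minimum of 10 imputed data sets will be generated". The treatment effect is pooled by Rubin's rules, and the plan looks at its p-value, "which will be declared statistically significant if < 0.05". The section explains why imputation is needed: "Missingness in outcomes is particularly acute because the univariate outcome is the average of 15 assessments".

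SAP 7.3.3 (persistence of shedding on Day 28) handles missing values in two stages. First, "Some missing data will be assumed positive or negative, as described for this day 28 shedding outcome in Section 5.4": a missing swab is taken as negative after cessation of shedding, or as positive if the participant was in hospital around Day 28. For the rest, "multiple imputation will be employed for subjects with still-missing values for the Day 28 viral shedding outcome". The floor is the same: "There will be a minimum of $m = 10$ imputed datasets". The signed root of the Cochran-Mantel-Haenszel statistic is pooled by Rubin's rules, and "The two-sided test will use $\alpha=0.05".

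SAP 5.5 provides for independent verification: "Two statisticians will each program all datasets and analyses for the DSMB reports and the primary manuscript(s) and the results will be compared".

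These sections state no seed, no rule for going above 10, no limit on Monte Carlo error, and no tolerance for comparing imputed results between programmers. No missingness rate or FMI is given for either outcome.

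**The concern.** Multiple imputation adds simulation noise on top of sampling noise. With 10 imputed data sets, the pooled estimate and the between-imputation variance are both estimated from only 10 draws. The same trial data, analysed twice with different seeds, give two p-values. If the result lies near the threshold, one run may be declared significant and the other not.

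Two of the four secondary outcomes are tested this way. The dual programming in 5.5 is also affected: if the two statisticians impute independently, a mismatch could be a programming error or chance, and the plan gives no means of telling which.

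**Working it through.** **Plan's own figure.** The SAP gives none for simulation error. The only sizing figures are in Protocol Table 2, for the primary outcome. They reproduce: at a 70% event rate, d = 400 × 0.70 = 280 and HR = exp(2.802/√(280/4)) = 1.398, against 1.40 stated. They do not bear on this point.

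**Inputs from the SAP.** Number of imputations m = 10 (7.3.2, 7.3.3), two-sided 0.05, Rubin's rules.

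**Assumptions.** FMI of 5% to 30%; 390 complete-data degrees of freedom (about 400 participants less model terms); the p-value that unlimited imputations would give (the limiting p-value).

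**Model.** Hold the trial data fixed and scale the total variance at unlimited m to 1. The between-imputation variance is then FMI and the within-imputation variance is U = 1 − FMI. Over seeds:

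- pooled estimate ~ N(z, FMI/m), where z is the limiting test statistic;
- estimated between-imputation variance B ~ FMI × χ²(m−1)/(m−1);
- T = U + (1 + 1/m)B, and p comes from a t distribution with Rubin's small-sample degrees of freedom;
- if a run is significant with probability a, two runs disagree with probability 2a(1 − a).

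**Hand check at FMI 20%, m = 10, limiting p = 0.03 (z = 2.170).**

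- SD of the pooled estimate = √(0.20/10) = 0.141.
- Typical T = 0.80 + 1.1 × 0.20 = 1.02. With about 118 degrees of freedom the critical t is 1.98, so the estimate must exceed 1.98 × √1.02 = 2.00.
- B also varies: its SD is 0.20 × √(2/9) = 0.094. The SD of T is 1.1 × 0.094 = 0.104, and that of the threshold is about 1.98 × 0.104/(2 × 1.01) = 0.102.
- Combined SD = √(0.141² + 0.102²) = 0.174, so a ≈ Φ(0.170/0.174) ≈ 0.84.
- Simulation gives a = 0.834, so disagreement = 2 × 0.834 × 0.166 = 0.277.

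**Simulated results, limiting p = 0.03.**

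| FMI | 95% range of p, m = 10 | Disagree, m = 10 | 95% range of p, m = 100 | Disagree, m = 100 |
|---|---|---|---|---|
| 5% | 0.021–0.045 | 1% | 0.027–0.034 | 0% |
| 10% | 0.018–0.054 | 9% | 0.026–0.037 | 0% |
| 20% | 0.013–0.074 | 28% | 0.024–0.040 | <0.1% |
| 30% | 0.010–0.096 | 39% | 0.022–0.044 | 0.6% |

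**Limiting p = 0.01, m = 10.** Disagreement is 0%, 0%, 0.4% and 3% at the same FMIs.

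**Error rates, averaged over trials.** Type I error at m = 10 is about 0.049 to 0.050 at every FMI. For an effect with nominal 80% power, m = 10 gives about 79.5% (FMI 5%) to 77.5% (FMI 30%); m = 100 gives about 80%.

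**What FMI is plausible for the symptom average?** An illustration used 200 participants per arm and assumed correlated daily scores:

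- 20% of days missing at random left about 3% complete cases but FMI of only 0.01–0.02;
- 40% of days missing gave 0.05–0.06;
- 15% of days missing plus 10% of participants with no daily scores at all gave 0.09–0.11;
- 15% of days missing plus 25% of participants with no daily scores gave 0.25–0.27.

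SAP 7.3.2 keeps a participant who has only a baseline score, so all 15 days can be imputed for one person. That is the pattern that raises the FMI.

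**The case against.** The case for leaving the plan alone is a good one, and much of it stands.

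- Ten is a minimum, so 100 is already allowed. True, but a floor with no rule leaves the number and the seed to be chosen at analysis.
- Rubin's rules include the (1 + 1/m) term and adjust the degrees of freedom, so the test is valid at m = 10. This stands, and the simulation confirms it.
- The effect is small away from the threshold. This stands. Averaged over trials at FMI 5% to 30%, two runs disagree in 1.0% to 2.9% of cases under the null and in 2.4% to 8.1% with 80% power.
- No finite number removes seed dependence. This stands. With a limiting p of exactly 0.05, two runs still disagree in 47% to 49% of cases at m = 100, although the p-values themselves lie much closer together.
- Both outcomes are secondary, and SAP 5.3 may make the shedding outcome exploratory if the primary is not significant, although its wording still names the outcome that was replaced. This lowers the stakes.
- A mismatch in dual programming would be seen and resolved. Probably so, but the plan does not say how.

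A reader might infer that the SAP regards missingness as acute for both outcomes. It says so only of the symptom average. For Day 28 shedding, fixed rules fill some gaps first, and nothing in the documents indicates a high FMI. Nor does acute missingness establish a high FMI for the symptom average: the reason given is that 15 assessments are averaged, and the illustration shows that few complete cases can go with a very low FMI.

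**Conclusion.** The point holds as a free improvement. With 10 imputations, the verdict on a borderline result can change with the seed alone. For a limiting p-value of 0.03 the chance that two runs disagree is about 1% at FMI 5% and rises to about 39% at FMI 30%; 100 imputations bring it under 1% across that range. At FMI 50% it would still be about 6.5% with 100. The power cost of using 10 is at most about 2.5 percentage points over the assumed range.

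The documents do not support the stronger conclusions that false positives are inflated or that significance of these outcomes generally depends on the seed. The sizes rest on an FMI that the documents do not give, on the assumed degrees of freedom, and on a result that happens to fall near 0.05.

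**What to change.** In SAP 7.3.2 and 7.3.3:

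- replace the minimum of 10 imputed data sets with 100;
- record the seed;
- report the Monte Carlo error, of the treatment estimate in 7.3.2 and of the pooled test statistic in 7.3.3, where no treatment estimate is pooled.

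In SAP 5.5, state that the two programmers share either the seed or the imputed data sets, so that a mismatch is not simply chance. Sharing a seed helps only if both use the same software and set-up. Sharing the data sets is surer, but the imputation code then needs its own check.

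The cost is computing time and a few lines of text. No data collection, sample size or choice of test changes.
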